B. YMSM: The consent process, enrollment, and baseline data collection takes place at two HIV clinic sites to describe the YMSM population in Baltimore. Patients are enrolled until 102 are enrolled at each site (85 are needed for analysis and the 102 allows for anticipated drop-out). Each patient completes 3 surveys approximately every 6 months at his regular clinic visit.

C. CURRICULUM Refinement: An initial curriculum is attached in ADDITIONAL DOCUMENTS. The educational team will continue to review, test, and incorporate elements of the curriculum being re-adapted for the US from international teaching efforts used in federally funded implementation efforts of HIV care and treatment. Site #1 will be the INTERVENTION SITE. Directors of Site #1 have chosen to have a day-long educational session for All-STAFF to be introduced to CASA Study activity. The curriculum is attached in ADDITIONAL DOCUMENTS prior to being offered to All STAFF participants.

PHASE 2: Staff Recruitment [NOTE this refers to CASA Team – the trainers to be trained]

Begins Month 13 (November, 2014) of the study.

A. STAFF – There are 2 types of STAFF participants: 1) CASA Team (Trainers) and 2) All STAFF who complete 2 surveys:

1. The CASA Team (Trainers) - Recruitment of the selected 5-8 member CASA Team made up of clinic STAFF trainers to receive the intervention: (1 physician or nurse practitioner; 2 nurses; 1 nursing assistant; 1 social worker or counselor; 1 outreach worker; and 1 administrative staff) at the intervention site. These will be selected by the clinic Administrative Team and the Research Team using the following criteria: all disciplines represented; each person chosen should have full understanding of how the clinic functions; each should be selected for leadership qualities and teaching or supervisory experience.

Participants are asked to avoid intentional sharing of study content to avoid contamination of the control site. for purposes of Staff at the control clinic will have the option to experience the training at the end of the study if it is shown to be beneficial.

B. YMSM: Enrollment and data collection continue as described in Phase 1.

C. Curriculum: Finalization of curriculum is on-going through-out the study as feedback from Site 1 is used for final revisions.

PHASE 3: Educational Intervention (See document attached in ADDITIONAL DOCUMENTS)

January-February, 2015

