Sample size calculations were made for logistic regressions predicting the likelihood of patients reporting viral suppression which indicates control of their disease (meaning that the patient is actually taking ART as prescribed). This is based upon the following assumptions: (1) improvement of 10% in patients reporting viral suppression by Follow-up #2 Survey among patients at Site 1 (experimental); (2) $1 - \beta = 0.8$; (3) $\alpha = 0.05$; and (4) $deff = 2.2$.

These analyses estimate the need for a total sample size of 170 (85 per site) at study end. Allowing for 20% attrition from Baseline to Follow-up 2 it will be necessary for us to accrue a total of 204 patients (102 at each site) in order to have a sufficient number of patients completing all 3 Patient Surveys. This number is higher than the number of patients we estimated to be required for the two-sample comparison of survivor functions using Cox Proportional Hazard regressions ($n=140$), (176) allowing for attrition. This sample size provides adequate power for the proposed longitudinal regression models. Based upon analyses made with N-Query Advisor 7.0 software 44 assuming $\alpha = 0.05$ and power $(1 - \beta) = 0.8$, the 170 cases completing Baseline, Follow-up 1 & Follow-up 2 will allow us to identify "small to medium" effects for the total model ($R^2 = 0.063$) and individual coefficients as well as a "medium" effect for up to each of 15 co-variates on R^2 (as small as 0.055) as outlined in Cohen (29).

The proposed sample size will allow us to estimate models including: a) a dummy variable noting the intervention arm, b) a term to correct for attrition bias, c) the baseline counterpart of the dependent (patient outcome) variable, and, d) a set of up to 12 relevant co-variates.

ENSURING ELIGIBLE PATIENTS:

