To assure that there would be a sufficient pool of potentially eligible patients at each of the study clinics to accrue the needed number of patients, we had each clinic review their clinic enrollment data to identify current clients who were potentially eligible for participation. We also identified patients at the UMB adolescent HIV clinic who are 16-17 years old but will be 18 by the end of study accrual and may move to one of the adult clinics. Based upon these reviews we estimate there will be an initial total of 135 potentially eligible patients at Site 1 and 185 at Site 2. Assuming participation rates of 75% at Site 1 and 55% at Site 2, we should easily be able to accrue the 204 patient participants required.

SAMPLE ATTRITION: This is a critical issue in longitudinal studies since there are numerous reasons participants may drop out. In YMSM, if attrition occurs non-randomly it can pose a threat to the ability to interpret the data. We address this by offering an honorarium at each survey and scheduling follow-up surveys at the next regular clinic appointment. We will also offer patients the option to complete follow-up surveys at a time that is most convenient for them. To further prevent loss to follow-up, following informed consent, we request names, addresses, and telephone numbers of up to 3 friends, neighbors, or relatives who will know how to contact them if we are unable to reach them in the future. We have extensive experience identifying and enrolling PLWH into observational and interventional research studies. Since clinics in this study have outreach workers, we are projecting a 20% loss to follow-up. If attrition is substantial, reasons for "drop out" will be analyzed for future implementation.

2 * Provide the plan for data analysis. Include in the description the types of comparisons that are planned (e.g., comparison of means, comparison of proportions, regressions, analysis of variance, etc.), which is the primary comparison/analysis, and how the analyses proposed will relate to the primary purposes of the study:

DATA ANALYSIS:

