View: v2_Clinical Trial Registration Information

Clinical Trial Registration Information

You indicated that this clinical trial has been registered.

1 * Was this trial registered at www.clinicaltrials.gov?

Yes No

2 If no, was this trial registered on a site other than clinicaltrials.gov?

Yes No

2.1 If Yes, specify the name of the other site:

2.2 Provide justification for registering this trial on this site:

3 * Registration Number

NCT02136680

ID: VIEW4E093BF1D0800
Name: v2_Clinical Trial Registration Information

View: v2_Participant Selection

Participant Selection

1 * How many local potential participants (or specimens/charts) do you anticipate will be screened for this study? **Screening includes determining potential participants' initial eligibility for and/or interest in a study.**

300

2 * How many participants (or specimens, or charts) will be enrolled/used for this study? **A local prospective participant is considered enrolled in the study when a UM-approved Informed Consent Document (not including separate screening consent forms) is signed.**

Local - the number being enrolled at this site:

284

Worldwide - the number being enrolled total at all sites (including local enrollment):

284

3 * Gender:

Male
Female

4 * Age(s):

18 years and older (Adult)

5 * Race/Ethnicity:

All Races Included

6 * Language(s):

English

6.1 Specify Other:

7 * Are you excluding a specific population, sub-group, or class?

Yes No

7.1 If Yes, indicate your justification for excluding a specific population, sub-group, class, etc.:

There are 2 populations enrolled in this study: (80 STAFF and 204 PATIENTS for total 284.)

LONGITUDINAL SURVEYS: PATIENTS (YMSM 18 - 35 yrs)

- 204 at 2 HIV clinics. Females are excluded as this is a study to describe the Baltimore population of HIV positive young men who have sex with men. It should be noted that some of these youth live and self-identify as "female" without truly being transgender and this population will be included in this study. The CICERO application does not allow for the answer of Transgender or cross-dressing.

ID: VIEW4E0E519C1D000
Name: v2_Participant Selection

View: v2_Vulnerable Populations

Vulnerable Populations

1 * Will you be including ANY of the following Vulnerable Populations? (Select all that apply)

Employees or Lab Personnel
Students

You may not include any members of the above populations as subjects in your research unless you indicate this here.

ID: VIEW4E0E519917800

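### The 20% attrition allowance multiplies 170 by 1.20 instead of dividing by 0.80, so 204 enrolled leaves about 163 completers, not 170

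*Combined protocol and SAP*

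**What the plan says.** All of this is in the combined protocol and SAP.

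- **Sample Size and Data Analysis, item 1, SAMPLE SIZE.** The logistic calculation for viral suppression ends with: "These analyses estimate the need for a total sample size of 170 (85 per site) at study end". The accrual target follows: "Allowing for 20% attrition from Baseline to Follow-up 2 it will be necessary for us to accrue a total of 204 patients", that is 102 at each site, "in order to have a sufficient number of patients completing all 3 Patient Surveys". The R-squared statements use the same count: "the 170 cases completing Baseline, Follow-up 1 & Follow-up 2 will allow us" to detect the effects listed. Between these, a Cox requirement is given: "using Cox Proportional Hazard regressions ($n=140$), (176) allowing for attrition".
- **Same item, SAMPLE ATTRITION.** The rate is repeated: "we are projecting a 20% loss to follow-up".
- **Justification, Objective, & Research Design, Phase 1.** The per-site pair reappears without a rate: "85 are needed for analysis and the 102 allows for anticipated drop-out".
- **Participant Selection, item 7.1.** The patient number feeds the overall enrolment: "80 STAFF and 204 PATIENTS for total 284".

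**The concern.** The 20% is defined as loss between Baseline and Follow-up 2. Its denominator is therefore the number enrolled, and the number to enrol is the required completers divided by 0.80. The plan instead adds 20% of the completer count to itself, which always under-enrols.

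The 170 is clearly a completer count. It is described as the number at study end and as the cases with all three surveys, and Phase 1 calls 85 per site the number needed for analysis. At stake is whether the plan's own attrition rate delivers the sample on which its logistic and R-squared power statements are based. The plan itself treats attrition as critical and the population as hard to retain, so a loss below the projected rate should not be assumed silently.

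**Working it through.** **Inputs.** Completers required: 170 (85 per site). Attrition: 20% from Baseline. Planned enrolment: 204 (102 per site). Alpha 0.05 and power 0.8. All are from the sample size section.

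**Reproducing the plan's figure.** With n completers and loss d:

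- n x (1 + d): 170 x 1.20 = 204 and 85 x 1.20 = 102. Both match exactly.
- n / (1 - d): 170/0.80 = 212.5, so 213; per site 85/0.80 = 106.25, so 107, or 214 in total. Neither matches 204.

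**What 204 delivers at 20% loss.** 204 x 0.80 = 163.2, and per site 102 x 0.80 = 81.6. The shortfall is 170 - 163.2 = 6.8, about 7 patients, or 6.8/170 = 4.0%.

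**Loss at which 204 does give 170.** (204 - 170)/204 = 34/204 = 16.7%.

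**Completers from 204 at other loss rates.**

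| Loss | Completers |
|---|---|
| 10% | 183.6 |
| 15% | 173.4 |
| 20% | 163.2 |
| 25% | 153.0 |
| 30% | 142.8 |

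**Effect on power (size only, not replacement values).** The plan gives no control-site suppression rate, so the 170 cannot be reproduced and no corrected power can be stated. The change can be bounded. With a two-sided 0.05 test (sidedness is assumed; the plan does not state it) and a normal approximation, power at 163.2 is Φ((1.96 + z) x √(163.2/170) - 1.96), where z is the normal quantile of the power at 170.

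- If power at 170 is 80%, it becomes 78.4%.
- For any power from 30% to 90% at 170, the drop is 1.0 to 1.8 points.

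For the R-squared tests the number of predictors must also be assumed:

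| Test | Power at 170 | Power at 163 |
|---|---|---|
| One covariate, R-squared 0.055, 15-predictor model | 0.878 | 0.864 |
| Total model, R-squared 0.063, 3 predictors | 0.810 | 0.791 |
| Total model, R-squared 0.063, 15 predictors | 0.486 | 0.464 |

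**The Cox figure.** It is not affected: 163 exceeds 140 if 140 counts completers, and 204 exceeds 176 if 176 counts accrual. The 176 is ambiguous. Dividing per site gives 70/0.80 = 87.5, so 88 x 2 = 176, whereas multiplying gives 140 x 1.20 = 168. If 176 is the attrition-allowed number, the same paragraph uses two different formulas. It may instead be a citation, since the plan cites references by number in parentheses. The finding does not depend on this.

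**Room to enrol more.** The plan's pools and participation rates give 135 x 0.75 + 185 x 0.55 = 101.25 + 101.75 = 203, already one short of 204 and about 10 short of 213 to 214.

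**The case against.** The arithmetic has no good defence. Reading the 20% as an oversample does not fit a loss stated from Baseline to Follow-up 2. The real objections concern weight.

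- **The consequence is small and the rate is a forecast.** Moving the loss from 10% to 30% shifts completers from 184 to 143, far more than the 7 at issue, and the 170 cannot itself be verified. This stands as a limit on size. It does not excuse a count that the stated rate contradicts.
- **Completing three surveys is not the only way into the analysis.** The GEE models can use patients with Baseline and one follow-up, viral suppression is also taken from the medical record, and data collected before withdrawal are kept. This softens the effect on the viral suppression analysis. It does not repair a target and power statements written in terms of 170 three-survey completers.
- **The R-squared statement is conditional on having 170.** That is true, but the plan presents 170 as what 204 enrolled will provide.
- **A re-run comes late.** Documents uploaded in January 2017 sit in an application for a study ending in March 2017. That argues against changing enrolment. It does not argue against correcting the figures that a report would repeat.
- **The 176 may be a citation.** It may; nothing here rests on it.

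**Conclusion.** The concern holds. At the plan's own 20% loss from Baseline, 204 enrolled gives about 163 completers (about 82 per site), not 170 (85 per site): 7 fewer, or 4%. The stated pair is consistent only if loss is at most 16.7%. The conclusion rests on two readings, both explicit in the text: the 20% is a share of those enrolled, and the 170 counts patients with all three surveys. It needs no outside figure. The expected loss of power is about 1 to 2 points, so this is a definite inconsistency of modest consequence that should be corrected. It does not threaten the study.

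**What to change.** 1. In SAMPLE SIZE, state either that 204 enrolled (102 per site) with 20% loss from Baseline gives about 163 patients (about 82 per site) completing all three surveys, or that 170 completers assumes a loss of at most 16.7%.
2. Base the logistic and R-squared power statements on 163. The sponsor should re-run them from the original inputs, including the control rate and number of predictors, rather than scale the present values.
3. Say whether 176 is a citation or the attrition-allowed Cox number. If it is the latter, use the same formula for both calculations.
4. Bring the 85 and 102 per site in Phase 1 into line.

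Enrolment need not change. Raising it to 214 would take the overall total from 80 + 204 = 284 to 80 + 214 = 294, and the plan's own participation rates (about 203 patients) would not support that.

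The cost is wording in two sections and one re-run of existing calculations, with no extra patients or data.

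### The detectable total-model R² of 0.063 at 80% power fits a model with about 3 predictors; with the maximum of 15 that the plan describes, power is about 49% and the detectable R² is about 0.107

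*Combined protocol and SAP*

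**What the plan says.** All the statements are in Sample Size and Data Analysis, question 1, under the sample size heading. The 170 completers (85 per site) come from a separate logistic-regression calculation for viral suppression. The plan then says that this number is also adequate for the longitudinal regression models and supports that with a second calculation:

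- The setting is "assuming $\alpha = 0.05$ and power $(1 - \beta) = 0.8". The number analysed is the 170 patients with all three surveys.
- The first effect, labelled small to medium, covers "effects for the total model ($R^2 = 0.063$) and individual coefficients".
- The second, labelled medium, is for each of up to 15 co-variates and is given as "as small as 0.055".

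The next paragraph lists what the models may contain. Three terms are fixed: the study arm, an attrition correction and the outcome's value at baseline. To these the plan adds "a set of up to 12 relevant co-variates". That is 3 fixed terms plus at most 12, so at most 15 predictors.

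The plan does not say how many predictors lie behind 0.063.

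**The concern.** The power of an overall test of R² depends strongly on the number of predictors, because the same explained variance is spread over more degrees of freedom. A detectable R² quoted without that number cannot be interpreted. The figure here stands beside a reference to 15 co-variates and just before a list that adds up to 15, so a reader will take it to describe that model.

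The two labels also suggest that the figures were not computed on one basis: the larger R² (0.063) has the smaller label, and the smaller one (0.055) has the larger label.

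What is at stake is how null results are read. If 0.063 is taken at face value, a non-significant overall model would be read as good evidence against an R² of that size. With the full model, the test would miss it about half the time.

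**Working it through.** **Inputs from the plan.** N = 170 completers, alpha = 0.05, power = 0.80 and total-model R² = 0.063. Number of predictors k: not stated for 0.063; the listed model gives 3 + 12 = 15 at most.

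**Method.** Overall F test that R² = 0 in multiple linear regression:

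- f² = R²/(1 − R²) = 0.063/0.937 = 0.0672
- noncentrality λ = N × f² = 170 × 0.0672 = 11.43
- power = P(noncentral F with k and N − k − 1 df, noncentrality λ, exceeds the 5% critical value)

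**Reproducing the plan's figure.** With k = 3 (df 3 and 166, critical F 2.66), power is 81.0%. The alternative convention λ = f²(N − k − 1) gives 80.0%. Solving for 80% power with the first convention gives R² = 0.0616. So 0.063 is reproduced at k = 3 and at no other k: 2 predictors give 86.0% and 4 give 76.7%.

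**The model as listed.** λ stays at 11.43; only the degrees of freedom change.

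| Predictors k | Power at R² = 0.063 | R² detectable at 80% power |
|---|---|---|
| 3 | 81.0% | 0.062 |
| 4 | 76.7% | 0.067 |
| 8 | 63.3% | 0.085 |
| 12 | 54.0% | 0.098 |
| 15 | 48.6% | 0.107 |
| 16 | 47.1% | 0.110 |

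The 16-predictor row covers the case in which the propensity term, required in the longitudinal analysis section, is not counted among the 12 co-variates.

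Check at k = 15: R² = 0.107 gives f² = 0.107/0.893 = 0.1198, λ = 20.37, critical F 1.73 and power 80.0%. To show the scale of the gap only, detecting 0.063 with 15 predictors would take 293 cases.

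**Variations at k = 15, R² = 0.063.** None rescues the figure:

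- λ = f²(N − k − 1): 43.9%
- random rather than fixed predictors (simulation): 48.3%
- alpha 0.10: 62.0%
- 0.063 read as f² rather than R²: 45.5%
- N = 204, the number enrolled: 59.0%

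**The single-covariate figure.** For a 1-df test in a 15-term model where the other terms explain nothing, an increment of 0.055 gives f² = 0.055/0.945 = 0.0582, λ = 9.89, df 1 and 154, critical F 3.90 and power 87.8%. The power is higher if the other terms explain something. The statement is true and conservative.

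**The case against.** The strongest reply is that the plan never attaches 15 predictors to 0.063. The number 15 belongs to the clause on single co-variates, and the model list says up to 12, so 15 is a ceiling. On that view 0.063 may have been computed for the three fixed terms, where it is correct, and the defect is only an unstated predictor count. This stands in part: what was entered in the software is not shown, and k = 3 is an inference. But power is already below 80% with one further term, and the plan offers the sample as supporting the full set. As written, the figure misleads for nearly every version of the model described.

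A second reply is that 0.063 could be an increment over other predictors. For 15 terms added to a base R² of about 0.4, power would be about 79%. The text says total model, however, and states no base R². Treating two follow-ups per patient as 340 independent rows would give 87%, but the plan counts 170 cases and expects repeated responses to be correlated.

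A third reply is that the overall F test decides little here, and this largely stands. The longitudinal section tests the intervention through a term for the arm, on one degree of freedom. Also, if the baseline outcome correlates 0.4 to 0.6 with follow-up (an assumption; the documents give no value), baseline alone gives R² of 0.16 to 0.36. Overall power with 15 terms is then about 97% to above 99.9%. That relief would not carry over to the residualised change scores planned in the longitudinal section if baseline is removed when the score is formed.

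A reader might go further and infer any of three things that the documents do not support:

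- *The intervention test is underpowered.* The 49% concerns the joint test of all terms. A 1-df increment of 0.055 has about 88% power or more.
- *The 0.055 should be replaced by 0.045.* The value 0.045 is the 80% point only if the other terms explain nothing. If they explain 0.063, 0.20 or 0.30, it becomes 0.042, 0.036 or 0.031. The plan states no such assumption, and 0.055 is not false.
- *Enrolment should rise towards 293.* The 170 was set by the viral-suppression calculation, not by this statement.

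**Conclusion.** The statement is wrong as written for the model described, but the matter is minor. A total-model R² of 0.063 with 170 completers has 80% power only with about 3 predictors. At the maximum of 15, power is about 49% and the detectable R² is about 0.107, so the stated value is about 41% below it ((0.107 − 0.063)/0.107).

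This rests on reading the figure as an overall F test in ordinary multiple regression, with 170 independent cases and alpha 0.05. The design effect of 2.2 that the section uses for the logistic calculation was not applied; applying it would lower power further. With fewer than 12 co-variates the shortfall is smaller, as the table shows.

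The error lies in a secondary sensitivity statement. It leaves the sample size derivation, the planned analyses and the test of the arm term untouched.

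**What to change.** In the sample size text:

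1. Restate the total-model figure as about 0.107 for 15 predictors, or say that 0.063 applies only to a model with 3 predictors. Either way, give the number of predictors.
2. Reconcile the size labels on 0.063 and 0.055, naming the effect measure and the test that each refers to.
3. Leave the single-covariate figure of 0.055 and the enrolment target as they are.

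The cost is a text edit of a few lines. The stated sensitivity of the overall model test becomes less favourable; data collection and analysis do not change.

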The early implementation of a palliative approach is a complex interdisciplinary approach that enhances communication at the point of care and requires integration of attitudes and skills with comprehension of the underlying illness, in addition to operative disease-specific delivery models.(103,139) In this study, the experience from implementation of the CASA curriculum in HIV care and treatment in international settings is evidence of its value as a management model for chronic illness.(6,43,47) This approach encourages effective engagement in care and goal setting with patients and with family carers.(48) The proposed study is in line with the need for research to document the process of forming and training interprofessional care teams and represents an important advance in the field.(9) Large-scale studies of the early integration of a palliative approach have been impeded by multiple factors related to size and organization of services.(1) With greater than 50% of clinical events and deaths experienced by PLWH despite their use of ART, clinicians must be more attentive to symptom management; evidence of effectiveness of PC exists for other chronic illnesses.(5,50,71) Only 18-28% of ALL HIV positive individuals in the US have documented viral control,(148) with Baltimore ranking among the cities with the lowest percentage with viral control, with only 14% of HIV infected adults having documented viral control.(53) Chronic disease impacts the well being of patients, their families/informal support systems and professional caregivers(74) and the World Health Organization cited "patient-centered care" as one of four necessary health reforms.(165) Emphasis is placed upon the need for full integration of broader health and social needs to avoid neglecting holistic health promotion activities.(26) Symptom burden alone has been correlated with quality of life.(42) An international HIV review noted the need for integrated: 1) pain and symptom management; 2) advance care planning; 3) psychosocial support; and 4) delineated patient, clinician, and service delivery care barriers regardless of antiretroviral (ART) usage.(66) Regardless of whether a prior history of substance abuse exists, pain, a symptom commonly experienced with HIV, causes disability, suffering, and impaired QOL is poorly addressed.(37,38,55)

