Second, through comparison of longitudinal data points, we will describe "change in time-varying patient characteristics", "stressors", "modifiers" and "outcomes".

"Attrition and balance" in key characteristics of the pre- and post-test groups will be assessed by comparing data from those completing: only baseline surveys; baseline and one follow-up; and baseline plus 2 follow-ups.

LOGISTIC REGRESSIONS: For viral suppression and other dichotomous potential correlates of study outcomes we will estimate several logistic regression models.

Given the longitudinal data collection with respondents repeatedly completing the same measures, patient reports for all measures are likely to be correlated. This violates the assumption of independence underlying logistic regression because it results in underestimates of standard error and therefore inaccurately increases the likelihood of rejecting the null hypothesis (Type-I error). To take into account higher intra-class correlation in the nested observations, we will use several generalized estimating equation (GEE) models with logit link.(167) The GEE model relates the marginal response $\mu_{it} = E(y_{it})$ to a linear combination of covariates by: $g(\mu_{it}) = x_{it}\beta$ and under logit link, $g(\mu_{it}) = \log(\mu_{it}/1-\mu_{it})$, where y_{it} is the indicator of viral status of the individual i at time t partner, and β 's are the estimated parameters. In this model specification, the covariance structure is treated as nuisance parameter. We will be using STATA 12, statistical software (147) for data cleaning and data analysis.

SURVIVAL ANALYSIS:

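### The allowance of up to 15 model terms rests on a linear-regression R-squared calculation and does not carry over to viral suppression, the binary outcome used to size the study

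*Combined protocol and SAP*

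**What the plan says.** All references are to the combined protocol and SAP.

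- **Sample Size and Data Analysis, item 1, SAMPLE SIZE.** The basis is a binary outcome: "Sample size calculations were made for logistic regressions predicting the likelihood of patients reporting viral suppression". The result is "These analyses estimate the need for a total sample size of 170 (85 per site) at study end". The section then reports detectable R-squared values for these 170 cases: 0.063 for the total model, and 0.055 for each of up to 15 covariates.
- **Same section, next paragraph.** "The proposed sample size will allow us to estimate models including" an arm indicator, an attrition term, the baseline value of the outcome and "a set of up to 12 relevant co-variates". The paragraph refers to the patient outcome in general and does not exclude binary outcomes.
- **Item 2, LOGISTIC REGRESSIONS.** "For viral suppression and other dichotomous potential correlates of study outcomes we will estimate several logistic regression models". GEE models with a logit link follow, to handle repeated records. No number of covariates is given there.
- **Item 2, internal validation.** There is a general caution about over-fitting, with bootstrap and permutation validation. It sets no limit on terms for binary outcomes and names no penalised method.

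The sample-size section gives no expected suppression rate, event count or events-per-term check.

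**The concern.** A detectable R-squared describes a continuous outcome, where information grows with the number of patients. In a logistic model, information is limited by the rarer of the two outcome categories. Maximum-likelihood coefficients are biased away from zero when that category is small relative to the number of terms. An R-squared figure therefore cannot show that 170 patients support 15 terms for viral suppression.

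What is at stake is the point estimate. A modest upward bias in the training log odds ratio would favour the intervention in a non-randomised comparison of two clinics, where the estimate already depends on covariate adjustment.

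**Working it through.** **1. The plan's R-squared figures.** Inputs: n = 170, alpha 0.05, power 0.80, all from the sample-size section. Method: noncentral F with f² = R²/(1 − R²) and noncentrality n·f².

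- A total R² of 0.063 corresponds to about three predictors, for which the detectable value is 0.0616.
- With 15 predictors the detectable total R² is 0.107, and power at 0.063 is 0.49.
- A single coefficient among 15 terms is detectable at 0.045, so the stated 0.055 is met (power 0.88).

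The per-coefficient figure holds for a continuous outcome. The total-model figure does not hold for 15 terms. Neither concerns a binary outcome.

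**2. Number of terms.** Arm 1 + attrition 1 + baseline outcome 1 + covariates up to 12 = 15.

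**3. Events per term, one record per patient at Follow-up 2.** Formula: min(suppressed, not suppressed)/15.

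- Ceiling at any rate: (170/2)/15 = 85/15 = 5.7.
- The background sections cite 14% for the city and 18% to 28% nationally. These are not design assumptions. As an illustration, take them as control rates and read the plan's 10% improvement as 10 points at Site 1:
  - 14%: 85 × 0.14 + 85 × 0.24 = 32.3, and 32.3/15 = 2.2.
  - 28%: 85 × 0.28 + 85 × 0.38 = 56.1, and 56.1/15 = 3.7.
- High suppression has the same effect. At a control rate of 80%, 144.5 are suppressed and 25.5 are not, so 25.5/15 = 1.7.

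**4. Events per term, GEE on repeated records.** The plan gives a design effect of 2.2 without saying what it represents. Assume that it reflects three waves with within-patient correlation 0.6 (1 + 2 × 0.6 = 2.2), so that two waves give 1.6.

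- Three waves: 510/2.2 = 232 effective records, and 232/2/15 = 7.7 at best.
- Two follow-ups, with baseline used as a covariate: 340/1.6 = 212.5, and 212.5/2/15 = 7.1 at best.
- Raw counts, ignoring clustering: 170/15 = 11.3 and 255/15 = 17.0.

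**5. Simulated bias, 15-term logistic model.** 85 patients per arm, a 10-point effect, and 2,500 runs per row. Covariate strengths are assumptions: the log odds ratio for baseline status and for each other covariate is shown.

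| Control rate | Baseline / covariate effect | Events per term | True log OR | Maximum likelihood (bias) | Coverage | Firth |
|---|---|---|---|---|---|---|
| 14% | 1.5 / 0.2 | 2.1 | 0.663 | 0.803 (+21%) | 0.940 | 0.677 |
| 28% | 1.5 / 0.2 | 3.6 | 0.455 | 0.530 (+17%) | 0.936 | 0.468 |
| 45% | 1.5 / 0.2 | 5.3 | 0.401 | 0.463 (+15%) | 0.939 | 0.414 |
| 45% | 0 / 0 | 5.3 | 0.399 | 0.446 (+12%) | 0.940 | 0.405 |
| 45% | 2.5 / 0.3 | 5.3 | 0.399 | 0.455 (+14%) | 0.946 | 0.398 |

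Across other assumed covariate structures and suppression rates from 14% to 80%, the bias ranged from 9% to 27%. Firth's method stays within about 3% of the truth in every row of the table.

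**6. Simulated bias, GEE.** 14 terms, null covariates, within-patient correlation about 0.56 to 0.59, 2,000 runs per setting. With two or three records per patient the log odds ratio was 7% to 10% too high, at both 45% and 14% control rates, with coverage of about 0.94.

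**7. Source of the imprecision.** In the 45% rows the standard error with arm alone is already 0.31. With 15 terms it is 0.34 to 0.44. Part of that rise is the usual effect of covariate adjustment in logistic models.

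**The case against.** The strongest reply is that the 15-term list is not assigned to the suppression model. It follows the R-squared sentence, resembles the residualized-change regressions later in item 2, and sets a ceiling. This stands in part. The text does not require a 15-term logistic model, but it covers patient outcomes without exception, and it comes directly after a calculation based on viral suppression.

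Several stronger readings are tempting, and the documents do not support them:

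- **That 5.7 caps the whole suppression analysis.** It applies to one record per patient. The planned GEE does better.
- **That 14% is the design rate.** The background text, "with only 14% of HIV infected adults having documented viral control", concerns infected adults in the city, whereas the study enrols clinic attendees.
- **That the main patient result is compromised.** Viral suppression sized the study, but it is one of several listed outcomes and is not named as primary.
- **That tests or intervals are invalid, or that power is lost.** Coverage stays near 0.93 to 0.95. In a check with 800 runs per setting and a true log odds ratio of 0.70, the 15-term model rejected more often than a three-term model (arm, baseline, propensity score) in all nine settings tried, for example 0.43 against 0.37 at 28% suppression.
- **That the model must be cut to four terms.** At 14% suppression, 170 × 0.14 = 24 events over four terms is 6 per term, close to the 5.7 in question. Dropping covariates also has a cost when clinics are not randomised.

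The plan's propensity scores, model-selection criteria and resampling checks are partial safeguards. They do not correct the small-sample bias of a maximum-likelihood fit.

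**Conclusion.** The point holds in a limited form. The 15-term allowance has no stated support for viral suppression, and the ceiling of 5.7 events per term at Follow-up 2 needs no outside figure. The expected consequence is a modest overstatement of the training log odds ratio: about 7% to 15% in favourable cases, and up to about 25% when the rarer outcome is near 14%. These percentages depend on assumed covariate strengths and correlations, and the GEE figures also on the assumed meaning of the design effect. Coverage is close to nominal, and most of the imprecision comes from having 170 patients. The point warrants a correction to the SAP text. It does not show that the suppression analysis is unusable.

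**What to change.** 1. Restate the 15-term sentence as applying to continuous outcomes only, and say how many predictors the total R-squared of 0.063 refers to.
2. For single-time-point logistic models of viral suppression with many covariates, specify a Firth-penalised likelihood.
3. Add a compact model (arm, baseline suppression, propensity score, attrition term) as a sensitivity analysis. It need not replace the fuller model.

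The cost is SAP wording and a little more analysis work, with no new patients, visits or data. Firth estimates will give slightly lower nominal rejection rates than the inflated maximum-likelihood fit.
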